This is a single-center, prospective cohort study of subjects undergoing clinically indicated PET/CT MPI, with documented coronary artery disease or an intermediate to high pretest likelihood of coronary artery disease. Following the clinical study, the research study is explained to the subjects. Consenting subjects will return on another day (next calendar day or later) for a repeat stress study with Lexercise or a repeat Lexiscan stress PET. Approximately 50 subjects (not more than 16 patients with normal Rubidium-82 or N-13 ammonia PETMPI, 10 healthy volunteers and 24 patients with reversible perfusion defects) will be enrolled in this study. After successful screening and enrollment, 13 random subjects (8 normal and 5 ischemic) will return for repeat Lexiscan PET, and 37 subjects will return for a Lexercise PET/CT MPI. Lexiscan PET will be performed per standard protocol. For Lexercise, a symptom limited exercise treadmill study with Lexiscan injection at peak exercise is performed. Rubidium-82 or N-13 ammonia will be injected and PET/CT images will be obtained in a list mode acquisition. Images will then be unlisted and myocardial blood flow computed.

Number of Subjects Planned

Approximately 50 subjects will be enrolled into the study.

Main Selection Criteria

Subjects will be eligible if they meet all of the following inclusion criteria and none of the exclusion criteria:

Inclusion criteria:

- Age > 18 years
- Clinically indicated Rubidium-82 or N-13 ammonia PET study
- Ten healthy volunteers recruited using web based advertisements.
- Known coronary artery disease (prior percutaneous coronary intervention, prior coronary artery bypass surgery or Q wave MI on ECG) or intermediate to high pretest likelihood of CAD
- Able to exercise on a treadmill
- Able and willing to provide informed consent to participate in the study

Exclusion criteria:

- Contraindications to exercise stress testing such as
 - unstable angina
 - known severe left main coronary artery stenosis
 - severe or uncontrolled heart failure
 - uncontrolled atrial or ventricular arrhythmias
 - symptomatic hypotension or severe hypertension (systolic blood pressure < 90 or > 200 mmHg, respectively)
 - > 1st degree atrioventricular block in the absence of a functioning pacemaker.
- Contraindications to Lexiscan use such
 - Allergy or intolerance to aminophylline or regadenoson

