primarily because exercise stress is not easy with PET. However, due to superior image characteristics, faster pace, and radiation dosimetry (compared to Thallium-201), exercise PET with Rubidium-82 is being viewed as an excellent alternative to exercise SPECT. This has become more important lately with the recent shortage of Technetium labeled radiotracers. Although exercise PET is feasible with Rubidium-82,² the workflow is challenging due to its short-half-life (75 seconds). Exercise PET with N-13 ammonia has been studied, but this is only possible in sites with an onsite cyclotron and the production and delivery of N-13 ammonia have to be coordinated with the PET scanner due to its 10 minute half-life.² Finally, in high volume nuclear cardiology laboratories, routine clinical use of exercise PET poses the concern of high radiation exposure to staff.⁵ This is primarily related to the fact that, after the PET radiotracer is injected on the treadmill, the staff is directly and closely exposed to the radioactive patient (while walking and positioning the subject to the scanner immediately after radiotracer injection).

Effects of exercise and vasodilator stress on myocardial blood flow:

Exercise is the most important physiological stimulus that increases myocardial oxygen demand. Exercise results in vasodilation of the normal epicardial coronary arteries (Figure, Top panel).⁶ The resultant increase in coronary blood flow and shear stress lead to endothelial release of nitric oxide and several other vasoactive mediators that cause further vasodilation of the downstream microvasculature and increased MBF. In contrast, diseased epicardial coronary arteries vasoconstrict in response to exercise resulting (Figure, bottom panel) in an increased flow gradient with reduced blood flow to the downstream microvasculature during exercise as compared to normal territories.

Wilson R. N Engl J Med 1996;334:1735-1737

Vasodilator stress agents do not typically result in vasoconstriction of diseased coronary arteries. They produce differential vasodilation of both normal and diseased coronary arteries by predominantly by an endothelium independent mechanism resulting in estimation of primarily endothelium independent changes in MBF, and to a lesser extent endothelium independent changes in MBF.⁷

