Combined standard symptom limited exercise stress testing with injection of Lexiscan at peak exercise (Lexercise PET) may be a novel protocol to optimally image maximal endothelium dependent (exercise) and endothelium independent (Lexiscan) alterations in MBF, using relative and absolute myocardial perfusion PET. Symptom limited exercise produces endothelial activation and vasodilation of normal and vasoconstriction of diseased coronary arteries. Addition of vasodilator stress at maximal exercise results in further (maximal) vasodilation of the normal coronary arteries; but minimal or no additional

vasodilation of the vasoconstricted diseased coronary arteries. This may result in improved defect contrast compared to the normal coronary arteries and better detection of CAD. Indeed a prior study demonstrated that defect size is larger with treadmill exercise stress compared to vasodilator stress with dipyridamole.⁸ Also, the precise reasons for larger perfusion defects with exercise compared to dipyridamole PET were not studied; although, true ischemia from exercise was proposed as a possible mechanistic link for larger perfusion defects with exercise. If endothelial dysfunction and true vasoconstriction are imaged with exercise PET, then, we can expect to metabolic abnormalities (switch from fatty acid to glucose metabolism) in the corresponding myocardial segments that may be imaged using tracers of fatty acid metabolism such as β Methyl-*p*-[123I]-iodophenyl-pentadecanoic acid (BMIPP) or C-11 Palmitate. Lastly, quantitative MBF is estimated predominantly with vasodilator stress and occasionally with bicycle exercise stress.⁹ Quantitative PET with Lexercise PET may be a novel method to image combined alterations in MBF related to both endothelium dependent and independent mechanisms of MBF.

II. SPECIFIC AIMS:

The overall purpose of the proposed research study is to examine in detail, using relative and quantitative Rubidium-82 or N-13 ammonia PET, the feasibility, safety, utility and the mechanistic basis of combined symptom limited exercise treadmill test with vasodilator stress compared to vasodilator stress alone in the evaluation of known or suspected coronary artery disease. The following specific aims are proposed:

Aim 1: To **assess the tolerability and safety** of the combined symptom limited exercise and Lexiscan protocol (Lexercise PET) compared to Lexiscan alone (Lexiscan PET).

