Hypothesis 1: Lexiscan will cause further/maximal vasodilation in a subject that is already vasodilated from exercise; therefore, the safety of this protocol needs to be ascertained. Lexiscan is expected to be well tolerated when injected during maximal exercise stress without any increase in major adverse events.

Aim 2: To **assess the image quality** of Lexercise PET compared to Lexiscan.

Hypothesis 2: Image quality as assessed by myocardial count density and heart to liver ratio will be superior with Lexercise compared to Lexiscan. However, misregistration artifacts from upward diaphragmatic creep will be higher with Lexercise compared to Lexiscan.

Aim 3: To compare **relative and absolute PET** with Lexercise compared to Lexiscan PET in identifying CAD.

Hypothesis 3: Lexercise PET offers the advantage of imaging reduced myocardial blood flow from vasoconstriction in diseased territories and maximal vasodilation in normal territories. Therefore, in patients with ischemic scans, the defect contrast on relative will be better with Lexercise compared to Lexiscan PET. We hypothesize that the differences in regional CFR between normal and abnormal territories will be greater with Lexercise compared to Lexiscan.

Significance of the mechanistic questions of this proposal:

The overall goal of this proposal is to evaluate the feasibility, utility and mechanistic underpinnings of a novel protocol incorporating combined maximal symptom limited exercise treadmill test with Lexiscan compared to Lexiscan alone. The combined standard symptom limited exercise stress testing with Lexiscan has several novel clinical and research applications:

1. This protocol provides exercise data (hemodynamic, electrocardiographic and clinical data) combined with high quality PET imaging that is important in patient management.
2. A PET MPI study can be performed with physiological exercise stress using any of the available flow tracers (Rubidium-82, N-13 ammonia, or the new compound BMS747158, an F-18 labeled agent) with minimal radiation exposure to the staff.
3. This protocol makes it feasible to assess both endothelium dependent (exercise) and endothelium independent (Lexiscan) mechanisms affecting MBF.

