- Hospital in-patients with request for pharmacologic stress: Attending physicians will be asked if they felt comfortable introducing the study to their subjects that they schedule for in-patient pharmacologic stress myocardial perfusion study verbally during their visit. If the physician introduces the study verbally, the subject will be asked if they would like to speak with a coordinator after the visit. If they would like to speak with someone, the coordinator will be notified and they will explain the study to the subject and go over the inclusion and exclusion criteria for the study. If they are interested in participating in the study an appointment will be made for their first visit.
- Special attention will be paid to enroll women and minorities in the study.
- Ten healthy volunteers will be recruited for this study using web based advertisements. They will all undergo Lexiscan (regadenoson) followed by Lexercise protocol (exercise + regadenoson) on a separate day.

b) Procedures for obtaining informed consent (including timing of the consent process)

For subjects interested in speaking to a study staff, Study PI, will go over the inclusion and exclusion criteria and will describe the study and procedures to the potential subject over the phone or in person. If the subject qualifies and is interested he/she is encouraged to discuss the study with his/her primary care physician or family members. Upon arrival for the study, the subject will be given a copy of the consent form to read. After the subject has finished reading the consent form, one of the physician investigators will describe the study in detail and answer any questions or concerns

the subject might have. If the subject agrees to participate in the study they will be asked to provide his/her written informed consent. Subjects will be given a copy of the signed consent form for their records. The investigator will inform the subject that they have the alternative not to participate in the study and can withdraw their consent at any point during the study.

The subjects will be given as much as 2 weeks to consider participation in the trial. Pregnant women and minors are excluded from this trial. Subjects that are determined by the physician to be unable to consent due to their physical or mental condition will not be enrolled in this trial.

V. STUDY PROCEDURES

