Rubidium-82 or N-13 ammonia PET image acquisition:

Following skin preparation and ECG lead placement, patient undergoes a symptom limited standard Bruce exercise treadmill test. At peak exercise (when patient is unable to exercise for more than 1 minute), the treadmill is stopped and patient is immediately positioned on the imaging table. Image acquisition is started with a CT scout image for positioning the heart (10 mA, AP scout, 9 seconds). Then 0.4 mg of regadenoson is given by intravenous push over 10 seconds followed by 10 ml of normal saline flush. Right after the saline flush, 40-60 mCi of Rubidium-82 or 20 mCi of N-13 ammonia is injected and emission imaging started in a list mode fashion started at the time of injection of radiotracer. Following completion of the emission imaging, a CT transmission scan (20 mA, 120 KV, non-gated, free tidal breathing) is obtained for correction of photon attenuation by soft tissues. .

Rest and Lexiscan stress images from the clinical study and the Lexercise stress emission images will be unlisted for analysis into a static file, a gated file and dynamic image frames (36 frames of 5 seconds each, 8 frames of 15 seconds each, and 6 frames of 30 seconds each for stress and 2 groups for rest of 24 frames at 5 seconds each and 8 frames at 30 seconds each). In subjects with serious or bothersome adverse effects, aminophylline will be administered intravenously (1 mg/kg, to a maximum of 150 mg) to alleviate the symptoms.

Myocardial blood flow quantification:

Myocardial blood flow (in ml/gm/min) at rest and after vasodilator stress will be quantified using a software based on GFADS and a 2 compartment model, developed and validated at the Brigham and Women's Hospital.¹³ Rest and peak stress myocardial blood flow will be computed in ml/gm/min and global and regional (vascular territories assigned as described below) coronary flow reserve computed by dividing stress myocardial blood flow by rest myocardial blood flow. Coronary vascular resistance at rest and stress will be computed by dividing mean aortic pressure [derived as 2 (diastolic blood pressure) + systolic blood pressure/3] by myocardial blood flow. In addition to calculating the myocardial blood flow for the left ventricle as a whole, myocardial blood flow will be determined for each of three vascular beds

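### A Lexercise–Lexiscan difference cannot be assigned to endothelial vasoconstriction: no exercise-only scan is made, and the coronary resistance that the plan computes is never compared between protocols

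*Combined protocol and SAP*

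**What the plan says.** Section II (Specific Aims) sets out to examine "the feasibility, safety, utility and the mechanistic basis of combined symptom limited exercise treadmill test with vasodilator stress compared to vasodilator stress alone". Hypothesis 3 in the same section gives the mechanism: "Lexercise PET offers the advantage of imaging reduced myocardial blood flow from vasoconstriction in diseased territories and maximal vasodilation in normal territories". From this it predicts better defect contrast and a greater regional CFR difference between normal and abnormal territories. The Significance list adds: "This protocol makes it feasible to assess both endothelium dependent (exercise) and endothelium independent (Lexiscan) mechanisms affecting MBF".

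The stress conditions imaged are these. After the clinical Lexiscan scan, patients return "for a repeat stress study with Lexercise or a repeat Lexiscan stress PET" (Synopsis, Design and Methodology). Of the healthy volunteers, Section IV says: "They will all undergo Lexiscan (regadenoson) followed by Lexercise protocol (exercise + regadenoson) on a separate day".

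Section V, Myocardial blood flow quantification, defines CFR as stress flow over rest flow. It also says: "Coronary vascular resistance at rest and stress will be computed by dividing mean aortic pressure" by flow, with the pressure "derived as 2 (diastolic blood pressure) + systolic blood pressure/3] by myocardial blood flow". The Study Endpoints list names flow and CFR but not resistance. Aim 3 appears twice, in the Synopsis and in Section VI. Both texts compare defect measures, flow, CFR and LVEF, and neither mentions resistance. Blood pressure changes appear in the endpoint list under safety and tolerability.

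**The concern.** Lexercise yields one stress flow value per territory. That value reflects oxygen demand, heart rate, perfusion pressure, any endothelial response, and the drug. The Background itself notes that "Exercise is the most important physiological stimulus that increases myocardial oxygen demand". Without an exercise-only scan, the Lexercise–Lexiscan difference is a net effect that cannot be split into endothelium-dependent and endothelium-independent parts.

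Resistance is the measure that would at least remove the pressure component. It is calculated, but no planned comparison uses it. If mean pressure is higher on the Lexercise scan, the absolute regional CFR difference grows, as Hypothesis 3 predicts, without any change in vascular tone. At stake is what the trial may conclude about mechanism from the flow and CFR results.

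**Working it through.** The plan states no figure on this point, so there is none to reproduce. The check has three parts.

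**1. What the design can separate.**
- Patients: Lexiscan, then Lexercise or repeat Lexiscan. Volunteers: Lexiscan, then Lexercise. Exercise alone is imaged in nobody.
- The repeat-Lexiscan group (13 subjects) informs repeatability, not mechanism.
- The Background mentions metabolic tracers that could show true ischaemia, but the Study Procedures do not include them.
- The patients' blood markers of ischaemia and the microRNA sample are not regional and have no place in Aim 3.

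**2. What pressure alone does to flow and CFR.**

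From the plan's definitions, resistance = mean pressure / flow, so stress flow = mean pressure / resistance, and CFR = stress flow / rest flow. Section V lists rest and Lexiscan stress images from the clinical study plus Lexercise stress images. For volunteers it places rest imaging at visit 2 only. Both CFRs therefore appear to share one rest flow. With stress resistance held fixed in each territory, every stress flow and every CFR is multiplied by

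k = mean pressure on Lexercise / mean pressure on Lexiscan.

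The absolute CFR gap (normal minus abnormal) is also multiplied by k. In the abnormal/normal ratio, k cancels.

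The documents give no stress pressures; those below are assumed.

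| Lexercise vs Lexiscan mean pressure (mmHg) | k | Gap of 1.0 becomes |
|---|---|---|
| 90 vs 90 | 90/90 = 1.00 | 1.00 |
| 100 vs 90 | 100/90 = 1.11 | 1.11 |
| 110 vs 90 | 110/90 = 1.22 | 1.22 |

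If pressure were lower on Lexercise, the gap would shrink (90 vs 100: k = 0.90).

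The same model with an assumed Lexiscan CFR of 3.0 in normal and 1.8 in diseased territory, and no vasoconstriction:

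| k | Normal CFR | Diseased CFR | Difference | Ratio |
|---|---|---|---|---|
| 1.0 | 3.00 | 1.80 | 1.20 | 0.60 |
| 1.1 | 3.30 | 1.98 | 1.32 | 0.60 |
| 1.2 | 3.60 | 2.16 | 1.44 | 0.60 |
| 1.3 | 3.90 | 2.34 | 1.56 | 0.60 |

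The difference widens, the ratio stays at 0.60, and flow in the diseased territory rises. A resistance comparison would show no change in any row.

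**3. Whether resistance is usable as printed.**

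The pressure formula lacks a bracket.
- At 120/80 mmHg, read literally: 2 × 80 + 120/3 = 200 mmHg. With (2 × diastolic + systolic)/3: (160 + 120)/3 = 93.3 mmHg.
- At 180/80 mmHg: literal 160 + 60 = 220; bracketed (160 + 180)/3 = 113.3.

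The literal form roughly doubles the pressure. It also compresses the change between these two readings: 220/200 = 1.10 against 113.3/93.3 = 1.21. The text does not say whether resistance is global or by territory, or at what moment pressure is taken. Section V places tracer injection after the treadmill stops, positioning, a CT scout and regadenoson, so peak-exercise pressure need not apply at injection.

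**The case against.** The other side has five arguments, and much of what they say stands.

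- *Pressure is not ignored.* Resistance is to be computed at rest and stress, and stress haemodynamics go on the datasheet. A reader might infer that the plan makes no allowance for pressure at all; the blood flow quantification text does not support that. The gap is narrower: the quantity is computed but not compared.
- *Pressure does not mimic the whole of Hypothesis 3.* A reader might infer that a pressure rise explains the entire predicted pattern. It does not. Uniform scaling raises diseased-territory flow, whereas the hypothesis speaks of reduced flow. It also leaves the diseased/normal ratio and relative defect contrast unchanged. The Synopsis version of Aim 3 compares defect with normal territory, so the direction of change in diseased tissue can be seen. Only absolute flow and the absolute CFR difference are exposed.
- *The pressure difference is unknown.* Tracer is given after exercise has stopped, and the Risks section notes mild falls in blood pressure with vasodilators. The true effect may be small or nil.
- *The operational aims do not partition mechanisms.* Aims 1 to 3 concern tolerability, image quality and perfusion, and no rule commits the investigators to report vasoconstriction. That a positive result would be so reported is conjecture. But the stated purpose and the Significance list do claim mechanism, so the limit on the conclusion should be written down.
- *Exercise-only PET is hard.* The Background gives workflow, cyclotron and staff-exposure reasons. These explain its absence; they do not supply the missing information.

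Resistance would not settle the mechanism either, because heart rate and demand also differ between the scans.

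**Conclusion.** The point holds as a limit on interpretation. The design can estimate the net effect of adding exercise to Lexiscan. It cannot attribute that effect to endothelium-dependent vasoconstriction, and the planned comparisons leave out the one computed measure that would remove perfusion pressure. Pressure alone would inflate absolute stress flow and the absolute regional CFR difference by 0% (equal pressures), 11% (100 vs 90 mmHg) or 22% (110 vs 90 mmHg). This rests on assumed pressures, fixed stress resistance, flow proportional to pressure (a simplification), and a shared rest scan, which the procedures imply but do not state. The documents do not support extending the point to the relative perfusion comparison, which is Aim 3's first analysis and the one its sample size refers to, or to the safety and image-quality aims. For a pilot this is a worthwhile and cheap correction, not a fault in the study's core comparisons.

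**What to change.** 1. In Aim 3, in both the Synopsis and Section VI, and in the endpoint list, add a paired Lexercise-versus-Lexiscan comparison of stress coronary vascular resistance by territory. Use blood pressure at tracer injection and mean pressure = (2 × diastolic + systolic)/3, and correct the printed formula.
2. Report the diseased/normal flow or CFR ratio beside the absolute difference.
3. State the Aim 3 conclusion as the net effect of adding exercise to Lexiscan. Label any endothelial interpretation hypothesis-generating, even if resistance differs, and bring the purpose, Hypothesis 3 and the Significance list into line.

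The cost is one more analysis of a quantity already computed, a pressure reading tied to injection time, and a more modest claim. No extra scan is needed.

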
Lexiscan PET. However, with PET MPI, imaging is started soon after stress while the subject is still breathing heavy and hence the effects on image quality, both relative PET and dynamic PET images need to be determined. A prior study² from the Ottawa heart institute, evaluated treadmill exercise PET with Rubidium-82. Myocardial uptake of Rubidium-82 was significantly greater with exercise compared with

dipyridamole stress (See Table reproduced from reference²). Higher ratios of myocardial uptake to gut, blood pool, and higher stress myocardial uptake were observed with exercise stress compared with dipyridamole stress. No significant differences in inferior wall defects due to misregistration were noted between exercise and dipyridamole stress studies using a dedicated PET scanner.

Rationale for specific aim 3:

A prior study,² from the Ottawa heart institute, evaluated treadmill exercise PET with Rubidium-82. This study included 50 patients (74% with known CAD and 26% with intermediate to high pretest likelihood of CAD) that underwent both exercise and dipyridamole Rubidium-82 PET within a median of 6 days of each other. More patients preferred exercise stress over dipyridamole. The summed stress (A), rest (B) and difference scores (C) were highly correlated (Figure below reproduced from reference²). Bland-Altman analysis revealed no significant differences in defect size between the treadmill and dipyridamole studies. Also, the agreement between treadmill and dipyridamole studies was similar to the agreement between repeat dipyridamole studies. The authors concluded that treadmill exercise 82Rb PET is feasible and provides imaging results of similar diagnostic content and better quality compared with dipyridamole stress.

In a separate study from the same group, treadmill exercise PET with N-13 ammonia was compared to dipyridamole PET.⁸ This study included 26 patients (41% with prior MI, 35% with prior PCI and 15% with prior CABG) that underwent both exercise and dipyridamole N-13 ammonia PET within a median of 6 days of each other. The summed stress, rest and difference scores were well correlated between the treadmill and dipyridamole studies. The defect size and severity was larger with treadmill exercise compared to dipyridamole PET (See Table below reproduced from reference⁸).

Table 3. Semi-Quantitative and Quantitative Analysis of N-13 PET Myocardial Perfusion Images

	Exercise Stress	Dipyridamole Stress	p Value	Correlation	Significance of Correlation
Summed stress score	9.1 ± 5.7	6.9 ± 5.9	<0.01	0.80	<0.001
Summed rest score	3.4 ± 3.3	3.2 ± 2.8	NS	0.79	<0.001
Summed difference score	5.8 ± 4.7	3.7 ± 4.6	<0.02	0.61	0.001
LV defect size (stress) (%)	19.3 ± 11.5	13.8 ± 13.6	<0.02	0.62	0.001
LV defect size (rest) (%)	8.1 ± 9.4	6.4 ± 6.5	NS	0.57	0.003

Values are mean ± SD.

LV = left ventricle; PET = positron emission tomography.

Myocardial count density of N-13 ammonia was significantly greater with dipyridamole compared to exercise stress. Successful performance of exercise ammonia required coordination between the cyclotron team and the imaging team. The authors concluded that treadmill exercise produces larger and more severe perfusion defects than dipyridamole and may reflect true ischemia.

III. STUDY METHODS

This is a single-center, prospective cohort study of subjects undergoing clinically indicated PET/CT MPI, with documented coronary artery disease or an intermediate to high pretest likelihood of coronary artery disease based on age gender and symptoms as described in the ACC/AHA/ASNC appropriate use criteria for cardiac radionuclide imaging.¹² Following completion of the clinical study, the research study is explained to the subjects. Consenting subjects will return on another day for a repeat stress study with Lexercise or a repeat Lexiscan stress PET. Approximately 50 subjects (not more than 16 patients with normal Rubidium-82 PETMPI and 34 with reversible perfusion defects) will be enrolled in this study. After successful screening and enrollment, 13 random subjects (8 normal and 5 ischemic) will return for repeat Lexiscan PET, and 34 subjects will return for a Lexercise PET/CT MPI, on the next calendar day or within 2 weeks of the clinical Rubidium-82 or N-13 ammonia PET study.

SUBJECT SELECTION

Main Selection Criteria

Subjects will be eligible if they meet all of the following inclusion criteria and none of the exclusion criteria:

Inclusion criteria:

- Age > 18 years
- Clinically indicated Rubidium-82 or N-13 ammonia PET study
- Ten healthy volunteers recruited using web based advertisements.

- Known coronary artery disease (prior percutaneous coronary intervention, prior coronary artery bypass surgery or Q wave MI on ECG) or intermediate to high pretest likelihood of CAD
- Able to exercise on a treadmill
- Able and willing to provide informed consent to participate in the study

Exclusion criteria:

- Contraindications to exercise stress testing such as
 - unstable angina
 - known severe left main coronary artery stenosis
 - severe or uncontrolled heart failure
 - uncontrolled atrial or ventricular arrhythmias
 - symptomatic hypotension or severe hypertension (systolic blood pressure < 90 or > 200 mmHg, respectively)
 - > 1st degree atrioventricular block in the absence of a functioning pacemaker.
- Contraindications to Lexiscan use such
 - Allergy or intolerance to aminophylline or regadenoson
 - Known severe or oxygen dependent bronchoconstrictive or bronchospastic lung disease [e.g., asthma, wheezing, chronic obstructive pulmonary disease (COPD), etc.].
 - Sick sinus syndrome
- History of heart transplantation.
- Dialysis
- Subject requires emergent cardiac medical intervention or catheterization after the clinical study.
- Documented myocardial infarction (MI) ≤ 30 days prior to enrollment.
- History of percutaneous coronary intervention (PCI) ≤ 4 weeks prior to enrollment.
- History of coronary artery bypass graft (CABG) ≤ 8 weeks prior to enrollment.
- Severe LV dysfunction, with ejection fraction of < 30%
- Serious non-cardiac medical illness (e.g., disseminated malignancy, severe neurological dysfunction at time of baseline PET study) or a social situation which will preclude research study participation
- History of seizure disorder

Discontinuation criteria:

Subjects should be discontinued for the following discontinuation criteria

- Subject does not fulfill inclusion or exclusion criteria

- Subject experiences a serious or intolerable adverse event
- In the Investigator's opinion, the subject is non-compliant with the protocol requirements (protocol violation)
- Subject's health would be jeopardized by continued participation
- Subject wishes to withdraw consent

Lexiscan will not be administered to patients with clinical or EKG evidence on ischemia during exercise treadmill testing. Clinical or EKG abnormalities during treadmill testing that would preclude administration of Lexiscan are listed below:

c) Clinical

- a. Severe chest pain
- b. severe lightheadedness or dizziness,
- c. severe shortness of breath
- d. exercise induced hypotension (> 10mm Hg decrease in systolic blood pressure)
- e. exercise induced hypertension (systolic blood pressure >210 mm Hg)

d) ECG changes

- a. Significant ST segment depression (≥ 2 mm)
- b. Significant ST segment elevation (≥ 1 mm)
- c. Sustained ventricular or atrial tachycardia,
- d. Exercise induced heart block

a) **Source of subjects and recruitment methods**

Patients will be recruited from the nuclear cardiology laboratory at the Brigham and Women's Hospital. Among them, stable and eligible patients meeting all inclusion and exclusion criteria will be invited to participate in this study and those who provide informed consent will be enrolled. Referring physicians will be informed about the study and asked to discuss the study with their patients being referred for PET myocardial perfusion imaging. Ten healthy volunteers will be recruited for this study using web based advertisements.

IV. SUBJECT ENROLLMENT

a) **Methods of enrollment including procedures for patient registration and or randomization**

The following recruitment methods will be used:

- This is a pilot study of subjects referred for a clinically indicated myocardial perfusion PET study. Majority of the subjects will be recruited from the clinical practices of the Brigham and

Women's hospital. The patients' referring physician will introduce the study to the subjects prior to the clinical PET study and those subjects that are willing to consider the study will be given the written informed consent for the study for review. Subjects' questions will be answered by [name]. There will be no time restriction to sign the consent form or participate in this study. Subjects that express an interest will be evaluated and provided they meet all the inclusion and exclusion criteria, they will be considered for this study.

- On occasion, we may identify subjects with reversible perfusion defects from our clinical Rubidium-82 or N-13 ammonia PET studies. In those instances, physicians requesting myocardial perfusion imaging studies (primary or specialist health care provider) will be contacted personally explaining the purpose of the study. The physicians of those subjects will be asked if they felt comfortable introducing the study to their subjects either verbally during the office visit or through a recruitment letter. If the physician introduces the study verbally, the subject will be asked if they would like to speak with a study physician after their appointment. If they would like to speak with someone, [name] will be notified and she will explain the study to the subject and go over the inclusion and exclusion criteria for the study. If they are interested in participating in the study an appointment will be made for their first visit.
- Hospital in-patients with request for pharmacologic stress: Attending physicians will be asked if they felt comfortable introducing the study to their subjects that they schedule for in-patient pharmacologic stress myocardial perfusion study verbally during their visit. If the physician introduces the study verbally, the subject will be asked if they would like to speak with a coordinator after the visit. If they would like to speak with someone, the coordinator will be notified and they will explain the study to the subject and go over the inclusion and exclusion criteria for the study. If they are interested in participating in the study an appointment will be made for their first visit.
- Special attention will be paid to enroll women and minorities in the study.
- Ten healthy volunteers will be recruited for this study using web based advertisements. They will all undergo Lexiscan (regadenoson) followed by Lexercise protocol (exercise + regadenoson) on a separate day.

b) Procedures for obtaining informed consent (including timing of the consent process)

For subjects interested in speaking to a study staff, Study PI, will go over the inclusion and exclusion criteria and will describe the study and procedures to the potential subject over the phone or in person. If the subject qualifies and is interested he/she is encouraged to discuss the study with his/her primary care physician or family members. Upon arrival for the study, the subject will be given a copy of the consent form to read. After the subject has finished reading the consent form, one of the physician investigators will describe the study in detail and answer any questions or concerns

the subject might have. If the subject agrees to participate in the study they will be asked to provide his/her written informed consent. Subjects will be given a copy of the signed consent form for their records. The investigator will inform the subject that they have the alternative not to participate in the study and can withdraw their consent at any point during the study.

The subjects will be given as much as 2 weeks to consider participation in the trial. Pregnant women and minors are excluded from this trial. Subjects that are determined by the physician to be unable to consent due to their physical or mental condition will not be enrolled in this trial.

V. STUDY PROCEDURES

The patient will have 1-2 study visits and healthy volunteers will have 2-3 study visits. Study visit 1 is the same for patients and healthy volunteers.

a. Study visit 1

- a. The subjects that are interested in the study will meet with [name] and go over the consent form and details of study participation.
- b. This screening visit will take about 1 hour. The research study team will ask the subject questions about medical history, medications, and prior hospitalizations to make sure that the subject qualifies for this study. Blood pressure, heart and breathing rates, temperature, and height and weight will be measured. Pregnancy is not allowed due to the unknown risks radioactivity may have on the mother or the unborn baby from the beginning of the study period through the end of the study. A blood pregnancy test will be performed on the day of the PET scan in women with child bearing potential.

Patients:

a. Study visit 2

The study visits 1 and 2 can be conducted on the same day. Study visit 2 is for the performance of the Lexercise stress Rubidium-82 or N-13 ammonia PET study. This will be scheduled at least the next calendar day or within 2 weeks of the clinical Rubidium-82 or N-13 ammonia PET study. While we aim to conduct the research scan within 2 weeks of the clinical scan, if there is a scanner malfunction or patient schedule conflict, we would like to extend the time frame for enrollment to 4 weeks.

Approximately 20 cc of blood will be drawn following completion of the Rubidium-82 or N-13 ammonia imaging study and evaluated for biochemical markers of ischemia.

b. Study Visit 3

Study visit 3 is for the performance of the Lexercise stress Rubidium-82 or N-13 ammonia PET study. This will be scheduled at least the next calendar day or within 2 weeks of the clinical Rubidium-82 or N-13 ammonia PET study. Approximately 20 cc of blood will be drawn following completion of the Rubidium-82 or N-13 ammonia imaging study and evaluated for biochemical markers of ischemia. A part of this blood sample (10 cc) will be sent to the laboratory of [name] for the isolation of microRNAs involved in angiogenesis and vascular inflammation. This blood sample will be stored for future analysis.

Healthy volunteers:

a. Study visit 2

The study visits 1 and 2 can be conducted on the same day. Study visit 2 is for the performance of the rest and regadenoson stress Rubidium-82 or N-13 ammonia PET study. No blood drawing will be performed during this visit.

